### 6.7.6. Derived Health Outcomes Endpoints

## 6.7.6.1. EQ-5D-5L

The EQ-5D-5L consists of the EQ-5D-5L descriptive system and the EuroQoL Visual Analogue Scale (EQ VAS). The descriptive system is comprised of five dimensions; mobility, self-care, usual activities, pain/discomfort, and anxiety/depression as shown in Table 11. Each dimension has 5 levels: no problems, slight problems, moderate problems, severe problems, and extreme problems. The respondent is asked to indicate his/her health state by ticking (or placing a cross) in the box against the most appropriate statement in each of the 5 dimensions. This decision results in a 1-digit number to express the level selected for that dimension. The digits for 5 dimensions can be combined in a 5-digit number to describe the respondent's health state. For example, 11122 would represent the health state for someone who has no problems with mobility, self-care, or usual activities, but who has slight pain or discomfort and slight anxiety or depression.

Note that this study uses the questionnaire in its validated form for subjects to report their health status "*today*". If the subject has had an HAE attack since their last visit, starting at Week 4, they complete it a second time to reflect on their health status during a "*usual attack*". On summary tables, the "*today*" and "*usual attack*" questionnaire results should appear in different rows.

Dimensions	Item
Mobility	I have no problems in walking about
	I have moderate problems in walking about
	I am unable to walk about
	I have severe problems in walking about
	I am unable to walk about
Self-care	I have no problems washing or dressing myself
	I have slight problems washing or dressing myself
	I have moderate problems washing or dressing myself
	I have severe problems washing or dressing myself
	I am unable to wash or dress myself
Usual activities I have no problems doing my usual activities	
(eg, work, study,	I have slight problems doing my usual activities
leisure activities)	I have moderate problems doing my usual activities
	I have severe problems doing my usual activities
	I am unable to do my usual activities
Pain/discomfort	I have no pain or discomfort
	I have slight pain or discomfort
	I have moderate pain or discomfort
	I have severe pain or discomfort
	I have extreme pain or discomfort
Anxiety/depression	I am not anxious or depressed
	I am slightly anxious or depressed
	I am moderately anxious or depressed
	I am severely anxious or depressed
	I am extremely anxious or depressed

 Table 11:
 EQ-5D-5L Dimensions (UK English Sample Version)

Abbreviations: EQ-5D-5L = EuroQoL 5-dimensional, 5-level questionnaire; UK = United Kingdom.

The EQ VAS records the respondent's self-rated health on a 20-cm vertical visual analogue scale (VAS). The VAS is numbered from 0 to 100 with 0 meaning 'the worst health you can imagine' and 100 meaning 'the best health you can imagine'. This information can be used as a quantitative measure of health as judged by the individual respondents. The EQ-5D-5L asks respondents to simply 'mark an X on the scale to indicate how your health is TODAY' and then to 'write the number you marked on the scale in the box below'.

For each subject and visit, the 5-digit health state will be converted into a single summary index, the EQ-5D Index, using the EQ-5D-5L Index calculator with US value set (van Hout, Janssen et al. 2012).

A manual for EQ-5D is available (van Reenen and Janssen 2015).

### 6.7.6.2. Treatment Satisfaction Questionnaire for Medication

The TSQM consists of 14 items of which 13 items are made up of 3 specific scales (effectiveness, side effects, and convenience) and a global satisfaction scale (global satisfaction). In addition, 1 item (Item 4) questions whether as a result of taking this medication, the subject experienced any side effects at all, which can be answered by yes or no. Scale scores are calculated for each scale and are transformed into scores ranging from 0 to 100, with higher scores indicating higher satisfaction.

The 14 questions are detailed in Table 12.

Table 12:List of Questions for TSQM

1ª	How satisfied or dissatisfied are you with the ability of the medication to prevent or treat your condition?
2 a	How satisfied or dissatisfied are you with the way the medication relieves your symptoms?
3 a	How satisfied or dissatisfied are you with the amount of time it takes the medication to start working?
4 b	As a result of taking this medication, do you currently experience any side effects at all?
5	How bothersome are the side effects of the medication you take to treat your condition?
6	To what extent do the side effects interfere with your physical health and ability to function (ie, strength, energy levels, etc.)?
7	To what extent do the side effects interfere with your mental function (ie, ability to think clearning, stay awake, etc.)?
8	To what degree have medication side effects affected your overall satisfaction with the medication?
9	How easy or difficult is it to use the medication in its current form?
10	How easy or difficult is it to plan when you will use the medication each time?
11	How convenient or inconvenient is it to take the medication as instructed?
12	Overall, how confident are you that taking this medication is a good thing for you?
13	How certain are you that the good things about your medication outweigh the bad things?
14 a	Taking all things into account, how satisfied or dissatisfied are you with this medication?

Abbreviations: TSQM = Treatment Satisfaction Questionnaire for Medication.

a These items are scaled on a 7-point bipolar scale from "extremely dissatisfied" to "extremely satisfied".

b Item #4 is a dichotomous response option with a conditional skip to Item #9.

Source: (Atkinson, Sinha et al. 2004)

The scale scores, also with higher numbers indicating higher satisfaction, are calculated as:

#### Effectiveness

 $([(Item 1 + Item 2 + Item 3) - 3] \div 18) \times 100$ 

If 1 item is missing:

 $([Sum of Available Items) - 2] \div 12) \times 100$ 

#### Side Effects

If Item 4 answer is "No" then score = 100.

Else:

 $([Sum of Item 5 to Item 8) - 4] \div 16) \times 100$ 

If 1 item is missing:

 $([(Sum of Available Items) - 3] \div 12) \times 100$ 

#### Convenience

 $([Sum of Item 9 to Item 11) - 3] \div 18) \times 100$ 

If 1 item is missing:

 $([(Sum of Available Items) - 2] \div 12] \times 100)$ 

#### **Global Satisfaction**

 $([Sum of Item 12 to Item 14) - 3] \div 14) \times 100$ 

If Item 12 or Item 13 is missing:

```
([(If Sum (the 2 Completed Items) - 2] \div 10) \times 100
```

If Item 14 is missing:

 $([Sum of Available Items) - 2] \div 8) \times 100$ 

If more than 1 item is missing from any subscale, then the subscale will not be calculated.

#### 6.7.6.3. Work Productivity and Activity Impairment Questionnaire

WPAI outcomes are expressed as impairment percentages, with higher numbers indicating greater impairment and less productivity (ie, worse outcomes). There are 4 impairment scores. The scoring is as follows (Reilly Associates 2002):

1. Absenteeism: Percent work time missed due to health:

$$100 \times [Q2 \div (Q2 + Q4)]$$

2. Presenteeism: Percent impairment while working due to health:

$$100 \times [Q5 \div 10]$$

- 3. Work productivity loss: Percent overall work impairment due to problem:  $100 \times \{Q2 \div (Q2 + Q4) + [(1 - Q2 \div (Q2 + Q4) \times (Q5 \div Q10)]\}$
- 4. Activity impairment: Percent activity impairment due to health:

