#### 53 CONFIDENTIAL

 $100 \times (Q6 \div 10)$ 

where,

Q2 = hours missed due to health problems

Q3= hours missed due to other reasons

Q4 = hours actually worked

Q5 = degree health affected productivity while working (circle a number from 0 to 10, where 10 is worst impairment)

Q6 = degree health affected regular activities (circle a number from 0 to 10, where 10 is worst impairment)

Q1 asks whether the individual works for pay (yes/no). If the answer to that question is 'No' then the subject is instructed to skip to Q6.

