# 9.3. Work Productivity and Activity Impairment

WPAI is a health outcomes endpoint for Part 1 and a secondary endpoint for Parts 2 and 3. Absenteeism, presenteeism, work productivity loss, and activity impairment will be calculated as described in Section 6.7.6.3. WPAI scores will be summarized descriptively by treatment group and visit for Part 1 and for the entire study period. For Part 1, MMRM will be used to compare each active dose to placebo for each time point. For this analysis, the change from baseline WPAI score of interest will be included as the dependent variable in the model with fixed effects for treatment, baseline attack value, baseline WPAI score, visit, visit by treatment interaction and a random effect for subject included as independent variables. An unstructured covariance structure will be used.

In addition, summaries statistics by treatment group and visit will be provided for responses to each individual question (Q2 to Q6) with a categorical summary provided for Q1.

Separate figures of each of the WPAI mean scores and change from baseline mean scores over time with 1 line per treatment group will be provided. There will be 1 set of figures for Part 1 and another for the entire study period. For the plots produced at the end of the study, the figure will have separate lines for active treatment for subjects originally randomized to placebo.

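### The WPAI work productivity loss formula in SAP 6.7.6.3 divides by Q10, an item the questionnaire does not have, so the score cannot be computed as printed

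*SAP*

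**What the plan says.** SAP 6.7.6.3 sets the scale for all the scores: "WPAI outcomes are expressed as impairment percentages, with higher numbers indicating greater impairment and less productivity". It then gives one formula per score. Absenteeism is Q2 over the sum of Q2 and Q4, times 100. Presenteeism is Q5 over 10, times 100. Activity impairment is Q6 over 10, times 100. The remaining score is labelled "Work productivity loss: Percent overall work impairment due to problem"; it adds to absenteeism a second term whose core is printed as "1 - Q2 \div (Q2 + Q4) \times (Q5 \div Q10".

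The item key below the formulas ends at Q6. The two rating items are "Q5 = degree health affected productivity while working (circle a number from 0 to 10, where 10 is worst impairment") and "Q6 = degree health affected regular activities (circle a number from 0 to 10, where 10 is worst impairment").

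Section 9.3 makes the formula operative: "Absenteeism, presenteeism, work productivity loss, and activity impairment will be calculated as described in Section 6.7.6.3". It compares each active dose with placebo on WPAI change from baseline by MMRM in Part 1. It also plans item-level summaries for "each individual question (Q2 to Q6) with a categorical summary provided for Q1".

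**The concern.** A scoring rule should be computable from the items collected. This one calls for an item that appears nowhere else in the SAP. The programmer must therefore depart from the text to produce the score, and nothing in the SAP records what the departure should be. Section 6.1 asks that the programs be documented well enough for outside statisticians to replicate the planned analyses. For this score, replication from the SAP text alone fails.

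The score is reported. WPAI is a Part 1 health outcome endpoint (Section 3.2.5), and durability of WPAI scores is a secondary endpoint in Parts 2 and 3 (Sections 3.2.7 and 3.2.9). It also feeds planned tables, listings and figures.

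**Working it through.** The SAP gives no worked score for this formula, so there is no stated figure to reproduce. The check compares the parts of the section with one another and then tests the repaired formula.

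**1. Does Q10 exist?**
- Item key in 6.7.6.3: Q1 to Q6.
- Item summaries in 9.3: Q1 (categorical) and Q2 to Q6.
- Neither place mentions a Q10, so the expression has an undefined input.

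**2. What was the divisor meant to be?**
- Presenteeism: 100 × [Q5 ÷ 10].
- Activity impairment: 100 × (Q6 ÷ 10).
- Q5 is rated from 0 to 10, so Q5/10 is the impairment fraction the formula needs. The constant 10 fits; an item response does not.

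**3. Are the brackets complete?** The full expression as it appears in the available text is

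100 × {Q2 ÷ (Q2 + Q4) + [(1 − Q2 ÷ (Q2 + Q4) × (Q5 ÷ Q10)]}

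It has four opening and three closing round brackets. The one before the 1 is still open when the square bracket closes. The expression already sits inside square brackets, so this round bracket does useful work only if it closes straight after (Q2 + Q4).

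**4. Does the repaired formula behave?** Write A = Q2/(Q2+Q4) and B = Q5/10. The repaired score is

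100 × [A + (1 − A) × B] = 100 × [1 − (1 − A)(1 − B)].

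A and B each lie between 0 and 1, so the score lies between 0 and 100%, and it rises with either component. That agrees with the scale stated at the top of 6.7.6.3. Two examples, with assumed answers:
- Q2 = 8, Q4 = 32, Q5 = 3: A = 8/40 = 0.20 and B = 0.30. Score = 100 × (0.20 + 0.80 × 0.30) = 44%.
- Q2 = 0, Q4 = 40, Q5 = 0: A = 0 and B = 0. Score = 0%, as it should be for a worker with no absence and no impairment.

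**The case against.** Four things can be said on the other side.

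- **The bracket may not be an error in the SAP.** The text was read from PDF by a program, and seven of the nine TSQM formulas in Section 6.7.6.2 also show unmatched brackets. This stands: the missing bracket is a query against the source file, not a finding. It does not explain Q10. In the same section the divisor 10 is read correctly in the presenteeism line, and an added letter Q is not the same kind of fault as a dropped bracket.
- **The intended rule can be recovered.** The section's own absenteeism and presenteeism formulas give the two components, and the SAP cites a WPAI scoring document. This largely stands and is why the fix is simple. The cited document is not available here, however, and Section 9.3 points to 6.7.6.3 for the calculation. A correct result would depend on an unrecorded departure from the SAP.
- **The stakes are low.** This stands. WPAI is not among the four endpoints in the testing hierarchy of Section 8.5, and Section 8.1 rules out hypothesis tests in Parts 2 and 3.
- **A programmer would notice.** Probably so, since an undefined variable stops the derivation. That limits the harm but is no reason to leave the line uncorrected.

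**Conclusion.** The Q10 divisor is a genuine error in an operative scoring rule: the work productivity loss score cannot be computed as printed. The missing bracket is likely but unconfirmed.

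The reach is one of four WPAI scores. The other three formulas are computable as written. No primary or multiplicity-controlled conclusion depends on this score. The conclusion rests on the SAP alone; the accompanying protocol is for Study BCX7353-202, while the SAP is for BCX7353-302, so it cannot be used to cross-check WPAI scoring.

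A reader might infer more: that the trial would report wrong scores, with every worker at 100% or above. That would need Q10 to be read as 10 and the missing bracket to be closed at the end of the term. The expression then becomes A + (1 − A × B), which runs from 100 to 200% once multiplied by 100. The documents do not support this as an expected outcome. As printed the formula returns nothing, this bracket position is the less natural of the two, and scores in that range contradict the section's own description of the outcomes as impairment percentages. No numerical bias should be attached to this point.

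**What to change.** Replace the formula in SAP 6.7.6.3 with

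100 × {Q2/(Q2+Q4) + [1 − Q2/(Q2+Q4)] × (Q5/10)}

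Check the bracket against the source file when making the change, and confirm that the programmed derivation uses this form. The cost is one line of text and a short programming check. No design, data collection or analysis model changes.

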#### 53 CONFIDENTIAL

 $100 \times (Q6 \div 10)$ 

where,

Q2 = hours missed due to health problems

Q3= hours missed due to other reasons

Q4 = hours actually worked

Q5 = degree health affected productivity while working (circle a number from 0 to 10, where 10 is worst impairment)

Q6 = degree health affected regular activities (circle a number from 0 to 10, where 10 is worst impairment)

Q1 asks whether the individual works for pay (yes/no). If the answer to that question is 'No' then the subject is instructed to skip to Q6.

## 6.8. Handling of Missing Data

# 6.8.1. Imputation of Missing Efficacy Endpoints Post Study Treatment Discontinuation

The attack rate used in the Part 1 primary analysis will be based on the observed data until the time of treatment discontinuation, if applicable. For the primary analysis at the end of Part 1, missing data sensitivity analyses will be conducted for handling of data for subjects who discontinue study treatment prior to the end of Part 1 in three ways:

- 1. Using observed post-treatment discontinuation data where available without imputation for missing data. For this analysis, the attack rate will be computed through the last date of observed data up to the Part 2 treatment start date/time, including data collected after treatment discontinuation.
- 2. Observed post-treatment discontinuation data will be used in combination with an imputed attack rate for the time period, post-treatment discontinuation, where data were not observed. An imputed rate for the entire 24-week period will be a weighted average of the observed rate up to the last day of diary collection (including days post treatment discontinuation) and the imputed rate for the time after treatment discontinuation during which data were not observed, with weighting based on the fraction of days with observed vs. unobserved data. For this rate, actual diary data collected after discontinuation of study treatment will be included in the observed rate where it is available by extending the time period in the denominator of the attack rate calculation to the last day that diary data were collected, even if past study treatment discontinuation. The only exception to this is if the subject started other prophylactic treatment after discontinuation of study treatment. In that case, actual diary data will be used up until the time of start of other prophylactic treatment.

For subjects for whom no diary data is missing post study treatment discontinuation, no imputation is necessary. An observed confirmed attack rate will be computed to include data post study treatment discontinuation as applicable, as long as the subject did not start other prophylactic therapy.

For subjects with missing data post study treatment discontinuation, missing data will be imputed as follows:

f = Fraction of Non-missing Data

Date of Last Day of Diary Collection Prior to Any Other Prophylactic Treatment – Date of First Dose + 1

169

robserved

As shown above, if a subject discontinues study treatment or withdraws from the study, the imputation of  $r_{imputed}$  will differ depending on whether the data are considered missing at random or not missing at random based on the reason for study treatment discontinuation or study withdrawal as shown in Table 13. Data missing at random will be imputed using multiple imputation with 10 separate founds of imputations, randomly selecting from observed confirmed attack rates of other subjects in the treatment group who completed the treatment for Part 1. Data not missing at random will be imputed using the median attack rate of subjects in the worst quartile of performance (ie, highest attack rate quartile) with regard to the primary endpoint for the given treatment group or the subject's observed rate over the time period of available data, if worse.

# Table 13:Reason for Study Treatment Discontinuation and Whether Data are
Considered Missing at Random or Not

Missing Data Considered Missing at Random	Missing Data Considered Not Missing at Random
Subsequent determination that inclusion/exclusion criteria were not met	Laboratory abnormality or adverse event
Intercurrent illness or emergence of new illness/medical condition/pregnancy	Discontinuation due to QT prolongation
Subject noncompliance with study drug or procedures	Discontinuation due to rash
Subject withdrew consent	Perceived lack of efficacy
Other a	Other a
Sponsor discontinuation a	Sponsor discontinuation a
Investigator judgment a	Investigator judgment a

a A review of discontinuations for Sponsor discontinuation, Investigator judgment, or other reason will be completed prior to unblinding of Part 1 data for determination of missing at random or not missing at random.

1. A tipping point analysis will be conducted using the observed data post treatmentdiscontinuation combined with imputed data for missing time periods. However, for tipping point analysis,  $r_{imputed}$  will be multiplied by a factor,  $\delta$ , for the active treatment group in the determination of the analyzed rate, as shown below. For the placebo group, there will be no such multiplicative factor. The tipping point is the value of  $\delta$  that leads to a reversal of a significant p-value. It shows how much larger than expected the attack rate would need to be for the time period of missing data for the active group in order to "tip" the significance level to non-significant. For tipping point analysis, the analyzed rate for the active treatment group is:

 $r_{analyzed} = f * r_{observerd} + (1 - f) * \delta * r_{imputed}$ 

For the placebo group, the analyzed rate would remain as:

 $r_{analyzed} = f * r_{observerd} + (1 - f) * r_{imputed}$ 

## 6.8.2. Other Sensitivity Analyses for Missing Data

The PP population analyses will serve as a sensitivity analysis for missing data by displaying the results of analysis for subjects who generally followed the protocol. Analysis of the primary efficacy endpoint based on the completers population will also serve as a sensitivity analysis for missing data by showing the attack rate in subjects who completed Part 1 of the study.

### 6.8.3. Missing Start and Stop Dates for Prior and Concomitant Medication

For analysis of medications, a complete date should be established to identify medication as occurring during treatment or not. For the purposes of handling partially reported start and stop dates for medication the following algorithm will be applied:

• Missing start day, but month and year present:

If trial medication had been taken in the same month and year as the occurrence of the medication, then the start day of the medication will be assigned to the day of first dose of trial medication.

Otherwise the start day will be set to the first day of the month.

• Missing start day and month, but year present:

If trial medication had been taken in the same year as the occurrence of the medication, then the start date of the medication will be assigned to the date of first application of trial medication.

Otherwise the start day and month will be set to 01 January.

• Missing end day, but month and year present:

The day will be set to the last day of the month.

• Missing end day and month, but year present:

The end day and month will be set to the date of trial termination.

However, if trial termination year is greater than the year of the event/medication, then the day and month will be set to 31 December.

• For paper diaries where the date of an acute concomitant medication is missing, the date will be imputed as the date of the attack.

In subject data listings, start and stop date of medication will be displayed as reported on the eCRF.

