# 4.4.2. Part 2 Randomization

At the Week 24 visit, subjects originally randomized to placebo in Part 1 will be randomized in a 1:1 (active:active) ratio to receive a 110 mg QD or 150 mg QD dose of BCX7353 in Part 2 (see Figure 2). Subjects will continue to receive the same dosing regimen received in Part 2 during Part 3. Once Part 1 results are available, all subjects in Part 3 may be moved to a single dose level of BCX7353, based on the data from Part 1, if appropriate.

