# 6.7. Derived and Transformed Data

## 6.7.1. Study Day

In this study, it is possible that the randomization date and date of first dose could differ. Study Day 1 is defined as the date of first dose.

If the date of measurement for a particular endpoint occurs on or after the first dose date, then study day will be calculated as:

(date of measurement - date of first dose) + 1

If the date of measurement occurs prior to the first dose date then study day will be calculated as:

date of measurement - date of first dose

There is no Day 0.

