## 6.8.4. Missing Start Date, Stop Date, Severity, or Relationship for Adverse Event

The same conventions to address incomplete dates for prior and concomitant medications will also be used for AEs. Should an event have a missing severity or relationship, it will be classified as having the highest severity and/or strongest relationship to study treatment.

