# 10.1. Adverse Event Preferred Term and System Organ Class Summary Tables

The following are Part 1 secondary endpoints and Part 2 and 3 primary endpoints:

- Number and proportion of subjects with a TEAE
- Number and proportion of subjects who discontinue due to a TEAE
- Number and proportion of subjects who experience a TESAE
- Number and proportion of subjects who experience a Grade 3 or 4 TEAE

AEs will be mapped to the MedDRA version 19.1 PT and system organ class (SOC). AEs are assessed by the Investigator as Grade 1 (mild), Grade 2 (moderate), Grade 3 (severe), or Grade 4 (life-threatening) according to Division of Microbiology and Infectious Diseases (DMID) using the November 2007 criteria. If a subject experiences multiple events that map to a single PT, the greatest severity grade according to the DMID criteria and strongest investigator assessment of relation to study medication will be assigned to the PT for the appropriate summaries. All AEs will be listed for individual subjects showing both verbatim and preferred terms.

TEAEs are defined as AEs that occurred on or after first dose of study treatment, whether in Part 1, 2 or 3, and will be assigned to the relevant treatment depending on when the TEAE began (Part 1 or Part 2 and 3 treatment). AEs occurring 30 days after the last dose for subjects who discontinue study treatment in Part 1 or up to 30 days after last dose in Part 2 or 3 will be considered as TEAEs and will be associated with Part 1, 2 or 3 respectively. Note that Investigators are not required to contact subjects after the last follow-up if it occurs prior to 30 days from last dose. All AEs that occurred prior to the initiation of study treatment or those recorded more than 30 days after the last dose of study treatment will be excluded from the tables but will be included in the listings.

Drug-related events are defined as those AEs that the Investigator believes were possibly, probably, or definitely related to the study drug.

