### 10.1.3. Missing and Partial Adverse Event Onset Dates

See Section 6.8.4.

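### For subjects who start on placebo, the rule for year-only AE start dates attributes events that arose on active drug to placebo

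*SAP*

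**What the plan says.** The rule has to be assembled from several sections of the SAP for Study BCX7353-302. The protocol supplied is for Study BCX7353-202 and has no bearing here.

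- **Year known, day and month missing (6.8.3).** The condition is "If trial medication had been taken in the same year as the occurrence of the medication". If it is met, "the start date of the medication will be assigned to the date of first application of trial medication"; otherwise 1 January is used.
- **Month and year known, day missing (6.8.3).** If trial medication was taken in that month, "the start day of the medication will be assigned to the day of first dose of trial medication"; otherwise the first of the month is used.
- **Extension to AEs (6.8.4).** "The same conventions to address incomplete dates for prior and concomitant medications will also be used for AEs". Section 10.1.3, on partial AE onset dates, adds only "See Section 6.8.4".
- **First dose (6.7.1).** "Study Day 1 is defined as the date of first dose". For Group 3 that dose is placebo.
- **Switch (4.4.2).** At Week 24, "subjects originally randomized to placebo in Part 1 will be randomized in a 1:1 (active:active) ratio" to 110 or 150 mg. Section 8.6.1 expects the first Part 2 dose on Day 169.
- **Attribution (10.1).** TEAEs "will be assigned to the relevant treatment depending on when the TEAE began (Part 1 or Part 2 and 3 treatment"). In the whole-study tables the placebo column holds Part 1 data only (Table 7).

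**The concern.** The date rule has a single anchor, the first dose of trial medication. Subjects who begin on placebo have two relevant first doses: placebo on Day 1 and active drug at about Day 169. Neither 6.8.3 nor 6.8.4 mentions the second. The SAP does recognise it elsewhere: 6.6 uses the first active dose in Part 2 to define baseline for these subjects, and 6.5.2 uses it to define treatment received. The omission from the date rule therefore looks like an oversight.

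For these subjects, an event on active drug with a year-only start date leaves the active columns and enters the placebo column. The subject-level proportions with any TEAE, a serious TEAE, a Grade 3 or 4 TEAE or a drug rash are primary endpoints of Parts 2 and 3. The rates per 100 person-years in 10.1.4 keep placebo and active exposure separate, so a moved event lowers the active rate and raises the placebo rate. Onset dates also feed the Kaplan-Meier summaries of time to rash and to GI events (10.1.2).

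The effect also runs against the rest of 6.8.4, which gives a missing severity or relationship its worst value.

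**Working it through.** The plan states no figure to reproduce. The check traces one subject and then enumerates dates.

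**One subject.** First (placebo) dose 5 March 2018. First Part 2 dose = Day 1 + 168 days = 20 August 2018. An AE that began in October 2018 on active drug but is recorded only as 2018 is dated 5 March 2018 and counted as placebo. One that began in 2019 and is recorded only as 2019 also becomes 5 March 2018 on the literal reading, because trial medication was taken in 2019; the reported year is overwritten.

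**Enumeration.** Inputs:
- first-dose dates: each of the 365 days of 2018, equally likely (assumption);
- first Part 2 dose: Day 169 (SAP 8.6.1);
- true AE onset: each day of Part 2 (Days 169 to 336), or of Parts 2 and 3 (Days 169 to 672).

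This gives 365 × 168 = 61,320 date pairs for Part 2 and 365 × 504 = 183,960 for Parts 2 and 3. An event is misattributed if its imputed date falls before the first Part 2 dose.

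*Year-only dates, true onset on active drug*

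| Reading of the rule | Part 2 | Parts 2 and 3 |
|---|---|---|
| Literal: any trial medication taken that year, so Day 1 | 61,320 / 61,320 = 100% | 183,960 / 183,960 = 100% |
| of these, imputed year differs from reported year | 42,252 / 61,320 = 69% | 164,457 / 183,960 = 89% |
| Narrower: Day 1 only if the first dose was in that year, otherwise 1 January | 47,124 / 61,320 = 77% | 66,430 / 183,960 = 36% |

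Under both readings, no year-only AE that truly began on placebo is moved to active (0 of 61,320 placebo-period pairs). For year-only dates the error has one direction.

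*Month and year known, day missing.* Only the calendar month of the switch can be misattributed.

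| Reading of the rule | Active to placebo, Part 2 | Active to placebo, Parts 2 and 3 | Placebo to active, Part 1 |
|---|---|---|---|
| First-dose day of the month inserted in the reported month | 1,358 / 61,320 = 2.2% | 1,358 / 183,960 = 0.7% | 1,432 / 61,320 = 2.3% |
| First-dose day only in the first-dose month, otherwise the first of the month | 5,373 / 61,320 = 8.8% | 5,373 / 183,960 = 2.9% | 0 |

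An example of the reverse error under the first reading: first dose 20 March 2018, Part 2 dose 4 September 2018. An AE that began on placebo on 2 September but is recorded as September 2018 becomes 20 September and is counted as active.

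**Effect of the proposed rule.** If a date compatible with Part 2 or later is resolved against the first Part 2 dose, no true active-period event goes to placebo under either type of partial date. The price, on the same grid, is that 47,124 / 61,320 = 77% of year-only and 5,373 / 61,320 = 8.8% of day-missing placebo-period events would be counted as active.

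**Number of events.** Let y be the number of year-only AEs that truly arose on active drug in these subjects. The number misattributed is y on the literal reading. On the narrower reading it is about 0.77y if they arose in Part 2, or 0.36y if they are spread evenly over Parts 2 and 3. The SAP gives no basis for y.

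**The case against.** The strongest objection is that y may be close to zero. The SAP requires at least weekly contact through Week 24 (Table 2), visits or calls at Weeks 26, 28, 32, 36, 40, 44 and 48, and contact every 4 weeks in Part 3 (4.1). It also provides edit checks and data cleaning with sites (6.3). An on-study AE known only to the year would be unusual, and without the Study 302 protocol or case report form we cannot tell whether a year-only start can be entered at all. This stands, and it limits the importance of the point.

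The endpoints also dilute the effect. They count subjects, so re-dating one event matters only if the subject has no other qualifying event in the column it leaves or enters. Parts 2 and 3 are descriptive, with no hypothesis tests (8.1). Subjects randomized to active drug in Part 1 cannot be moved between arms by this rule, although their onset may be placed too early. All of this stands.

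A reader might infer that every partial date moves events from active to placebo, or that a month-known AE is carried back to Day 1. The text does not support either. The month-known branch imputes only the day, so the reported month is kept. If the first-dose day of the month is inserted, the errors are about equal in the two directions (1,358 against 1,432 onset days).

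Finally, attributing ambiguous events to active drug introduces an opposite bias. That is true and is a deliberate choice; it follows the worst-case principle that 6.8.4 already uses.

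**Conclusion.** The point holds for year-only AE start dates in subjects who were on placebo in Part 1. There the stated rule gives a wrong attribution, always from active to placebo: for all true active-period events on the literal reading, and for about 77% (Part 2) or 36% (Parts 2 and 3) on the narrower one. That two programmers could obtain such different answers from the same text is itself a reason to clarify it. For dates missing only the day, the risk is confined to the switch month, and its direction depends on how the day of first dose is read.

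The percentages are conditional on a partial date and assume evenly spread first doses, a switch on Day 169 and uniform onset. About 40 placebo subjects are planned, and fewer will enter Part 2 after dropout. A reader might want to put a count on the affected events, but the SAP gives neither an AE total nor a frequency of partial dates, so any count would be an assumption. The number is probably small. This is a minor correction that affects no efficacy analysis.

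**What to change.** Add two sentences to SAP 6.8.4, for AEs only:

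1. A reported month or year of onset is never overridden by imputation.
2. For subjects randomized to placebo in Part 1, a partial start date compatible with Part 2 or later is resolved against the first Part 2 dose and attributed to the active treatment then received.

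It would help to say that compatibility takes account of any known stop date, so that an event that ended before the first Part 2 dose stays with placebo. The medication rule in 6.8.3 can stay as it is.

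The change needs no new data and only a small edit to the AE date derivation. Its cost is that some ambiguous placebo-period events will be counted as active. That is conservative for safety. Listing the AEs with imputed start dates in these subjects would let a reader see how many are involved.
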